## 1. HISTORY OF CHANGES

All versions of the document have to be documented in the table of history of changes. The owner of the document has to act in accordance with the latest version of the document.

Status	Version	Effective Date (10-FEB-2017)	Change description
Current version	1.0		First version

**Protocol code:** D-FR-10380-002

**Protocol Title:** A phase IIA, open-label, single-arm, two stage, multi-centre study to investigate the pharmacodynamics, pharmacokinetics, safety and tolerability of repeated subcutaneous administration of BIM23B065 in subjects with acromegaly

## 2. ABBREVIATIONS

Acronyms, Abbreviations, Initials	Description / Explanation
ACC	Accelsiors CRO and Consultancy Services
ACTH	Adrenocorticotrophic Hormone
ADA	Anti-Drug Antibodies
AE	Adverse Event
BID	Bis in die (twice a day)
BP	Blood Pressure
BS	Biostatistics
CBC	Complete Blood Count
Core Review Team	Consists of Project Manager, Head of Drug Safety Unit, Clinical Data Manager, Biostatistician
CSR	Clinical Study Report
DBP	Diastolic Blood Pressure
DLT	Dose Limiting Toxicities
DM	Data Management
DMP	Data Management Plan
DNA	Deoxyribonucleic acid
DRC	Data Review Committee
DSMB	Data and Safety Monitoring Board
D 2	Dopamine Receptor Sub-type 2
ED	Early Discontinuation
EE	Efficacy Evaluable

**Protocol code:** D-FR-10380-002

**Protocol Title:** A phase IIA, open-label, single-arm, two stage, multi-centre study to investigate the pharmacodynamics, pharmacokinetics, safety and tolerability of repeated subcutaneous administration of BIM23B065 in subjects with acromegaly

Acronyms, Abbreviations, Initials	Description / Explanation
EoS	End of Study
FDA	United States Food and Drug Administration
FSH	Follicle Stimulating Hormone
FT4	Free Thyroxine
FU	Follow Up
GCP	Good Clinical Practice
GH	Growth Hormone
HR	Heart Rate
ICU	Intensive Care Unit
IGF-1	Insulin-like Growth Factor-1
IMP	Investigational Medicinal Product
ITT	Intent-To-Treat Population
LH	Luteinizing Hormone
mITT	Modified Intent to Treat
NA	Not Applicable
PD	Pharmacodynamics
PK	Pharmacokinetics
PM	Project Manager
PP	Per-Protocol Population
PRL	Prolactin
QA	Quality Assurance
QC	Quality Control
RA	Regulatory Authority

**Protocol code:** D-FR-10380-002

**Protocol Title:** A phase IIA, open-label, single-arm, two stage, multi-centre study to investigate the pharmacodynamics, pharmacokinetics, safety and tolerability of repeated subcutaneous administration of BIM23B065 in subjects with acromegaly

Acronyms, Abbreviations, Initials	Description / Explanation
RNA	Ribonucleic Acid
SBP	Systolic Blood Pressure
SAE	Serious Adverse Event
SAP	Statistical Analysis Plan
SIV	Site Initiation Visit
SMP	Study Management Plan
SOP	Standard Operating Procedure
SSTR 2	Somatostatin Receptor 2
SSTR 5	Somatostatin Receptor 5
TEAE	Treatment-emergent AE
TID	Ter in die (Three times a day)
TSH	Thyroid Stimulating Hormone
WIN	Work Specific Instruction

**Protocol code:** D-FR-10380-002

### 3.2. Scope

This SAP applies to all planned statistical analyses performed by Accelsiors Biometrics. Details regarding PK and PK/PD modelling will be described in a separate Pharmacometric Analysis Plan. Any other statistical tasks, which are not analysis-related (e.g. Protocol and CRF Review) are out of the scope of this plan. These tasks are described in detail in the applicable BS SOPs and WINs.

Activity/Task	Sponsor/ 3rd Party Vendor	ACC	N/A
Interim statistical analyses		X	
Final statistical analyses		X	
PK analysis	X		
PK/PD analysis	X		

### 3.3. Purpose

The purpose of this SAP is to outline the planned analyses to be completed to support the completion of the Clinical Study Report (CSR) for protocol D-FR-10380-002. The planned analyses identified in this SAP will be included in regulatory submissions and/or future manuscripts. Also, exploratory analysis not necessarily identified in this SAP may be performed to support the clinical development program. Any post-hoc, or unplanned analysis not identified in this SAP will be clearly identified in the respective CSR.

### 3.4. Preparation, Review and Changes to the SAP

The SAP will be prepared by ACC Biostatistician for submission to ACC PM and to the Aepodia S.A. and Ipsen Pharma SAS study team for review and input. Final approval is given by the ACC Chief Scientific Officer and by the head of statistics of Ipsen Pharma SAS. The SAP needs to be finalized before the first patient first visit.

SAP is subject to the periodic review as appropriate in relation to the trial status. The authoring, review and approval of SAP revisions will follow the same process as for the initial version. Review may result in possible extension, modification or replacement in the form of an Appendix, Amendment, or Revision.

**Protocol code:** D-FR-10380-002

**Protocol Title:** A phase IIA, open-label, single-arm, two stage, multi-centre study to investigate the pharmacodynamics, pharmacokinetics, safety and tolerability of repeated subcutaneous administration of BIM23B065 in subjects with acromegaly

The core review team is responsible for ensuring that after any changes all sections of the Statistical Analysis Plan will be harmonised.

### **3.5. Changes to the Protocol**

In case the clinical study protocol undergoes a major amendment affecting statistical analyses procedures then a new version of the SAP will be issued.

Authoring, review and approval process of new SAP versions will be the same as for the initial version.

## **4. PREFACE**

This Statistical Analysis Plan (SAP) describes the planned analysis and reporting for Ipsen Pharma SAS protocol D-FR-10380-002 (A phase IIA, open-label, single-arm, two stage, multi-centre study to investigate the pharmacodynamics, pharmacokinetics, safety and tolerability of repeated subcutaneous administration of BIM23B065 in subjects with acromegaly). This phase IIA study is being carried out to assess pharmacodynamics, safety and tolerability of BIM23B065 for the treatment of acromegaly. The structure and content of this SAP provides sufficient details to meet the requirements identified by the FDA and International Conference on Harmonisation of Technical Requirements for Registration of Pharmaceuticals for Human Use (ICH): Guidance on Statistical Principles in Clinical Trials. The following documents were reviewed in preparation of this SAP:

- Clinical Study Protocol D-FR-10380-002 issued 27 July 2016.
- Clinical Study Protocol version 2, D-FR-10380-002 issued 14 September 2016.
- CRF Module Plan 1.1. for Protocol D-FR-10380-002.

## **5. STUDY OBJECTIVES AND ENDPOINTS**

### **5.1. Study Objectives**

#### **5.1.1. Primary Objective**

- To assess the pharmacodynamics (PD) of repeated administration of BIM23B065 in reducing growth hormone (GH) in subjects with acromegaly.

**Protocol code:** D-FR-10380-002

**Protocol Title:** A phase IIA, open-label, single-arm, two stage, multi-centre study to investigate the pharmacodynamics, pharmacokinetics, safety and tolerability of repeated subcutaneous administration of BIM23B065 in subjects with acromegaly

### 5.1.2. Secondary Objectives

- To assess the safety and tolerability of repeated administration of BIM23B065 in subjects with acromegaly.
- To assess the pharmacokinetics (PK) and PD of repeated administration of BIM23B065.
- To investigate the PK of BIM23B133 which is the major metabolite of BIM23B065.
- To assess the correlation of BIM23B065 exposure with blood pressure (BP) and heart rate (HR).

### 5.1.3. Exploratory Objectives

- To correlate GH, Insulin-like Growth Factor-1 (IGF-1) and Prolactin (PRL) responses with expression of Somatostatin Receptor 2 (SSTR2), Somatostatin Receptor 5 (SSTR5) and Dopamine receptor sub-type 2 (D2) in pituitary tumour tissues, when available.
- To assess anti-drug antibodies (ADA).

### 5.1.4. Biobanking

- To explore potential utility of biomarkers for association with drug activity, adverse events (AEs), to explore drug mechanism of action and/or disease understanding. Serum/plasma, whole blood samples will be collected for deoxyribonucleic acid (DNA) and whole blood samples for ribonucleic acid (RNA).

## 5.2. Study Endpoints

PD endpoints are primary and PK and safety are secondary endpoints in this study. PD and safety endpoints are further described below. PK endpoints, PK and PK/PD analyses are detailed in a separate Pharmacometrics Analysis Plan document.

### 5.2.1. Primary Endpoints and Evaluations

- The proportion of subjects with GH  $\leq 2.5\mu\text{g/l}$  or  $>50\%$  reduction from mean baseline GH (measured over 6 hours on Day -1) after 6-day titration plus 8-day treatment with BIM23B065 measured by mean serum concentration of GH over 6-hours on Day 14.

### 5.2.2. Secondary Endpoints and Evaluations

- Assessment of safety and tolerability.
- Assessment of the proportion of subjects with GH  $< 1.0\mu\text{g/l}$  after 6-day titration plus 8-day treatment with BIM23B065 measured by mean serum concentration of GH over 6-hours at Day 14.
- Determination of the efficacy of BIM23B065 in reducing IGF-1 to  $< \text{ULN}$  (age normalised) after 6 day-titration and 8-day treatment period at Day 14 and Day 28.

*Statistical Analysis Plan*

*SD-BS-014, version 1.0*

*Parent document: SOP-BS-005*

*Page: 13 of 37*

**Protocol code:** D-FR-10380-002

**Protocol Title:** A phase IIA, open-label, single-arm, two stage, multi-centre study to investigate the pharmacodynamics, pharmacokinetics, safety and tolerability of repeated subcutaneous administration of BIM23B065 in subjects with acromegaly

### **5.2.3. Exploratory Endpoints and Evaluations**

- Assessment of ADA.
- Exploration of the relationship between response to BIM23B065 and the expression of SSTR2, SSTR5 and D2 in those subjects with available tumour tissue.

### **5.2.4. Safety Endpoints and Evaluations**

- Adverse Events.
- Vital signs (supine and standing BP and HR).
- 12-lead ECG and ECG monitoring by 3-lead Holter device at specific timepoints, QTc interval will be calculated using Fridericia methodology.
- Clinical laboratory assessments: haematology, coagulation, clinical biochemistry including glucose, glucagon and insulin measurements, urinalysis.
- Putative antibodies to BIM23B065.
- Endocrine parameters: Adrenocorticotrophic Hormone (ACTH), Cortisol, Luteinizing Hormone (LH), Follicle Stimulating Hormone (FSH), Free Thyroxine (FT4), Thyroid Stimulating Hormone (TSH) and Testosterone (for males only), .
- Gallbladder echography.

### **5.2.5. Pharmacodynamics and Pharmacokinetics Endpoints and Evaluations**

- PD Assessments:
  - Mean serum concentration of GH over 6 hours at baseline (Day -1), Day 7 and Day 14.
  - IGF-1 levels at baseline, Day 14 and Day 28.
  - PRL levels over 6 hours at baseline, Day 7 and Day 14.
- PK Assessments:
  - Time points will follow a sparse PK sampling approach. On day 7 (first day of 1.0mg) pre-dose, 0.5h, 1h, 2h, 4h and 6h post-morning dose. On day 14 (last day of 1.0mg) pre-dose, 0.5h, 1h 2h, 4h and 6h post-morning dose.
  - One random sampling for PK analysis will also be taken at further routine study visits (Day 10) to co-ordinate with safety and PD assessments.
  - Drug (BIM23B065) and its major metabolite BIM23B133.

**Protocol code:** D-FR-10380-002

**Protocol Title:** A phase IIA, open-label, single-arm, two stage, multi-centre study to investigate the pharmacodynamics, pharmacokinetics, safety and tolerability of repeated subcutaneous administration of BIM23B065 in subjects with acromegaly

### 5.2.6. Biobanking Endpoints and Evaluations

To biobank whole blood samples for DNA at baseline pre-dose (Day -1), serum/plasma and whole blood samples for RNA at baseline pre-dose (Day -1), at Day 14 and Day 28 (EoS/ED).

## 6. STUDY METHODS

### 6.1. Overall Study Design and Plan

This is an open-label, non-randomised, multi-centre, adaptive two-stage phase II study.

During Stage 1, up to 12 subjects will be enrolled to receive BIM23B065 BID for two weeks. The primary endpoint will be the proportion of subjects with GH  $\leq 2.5$   $\mu\text{g/l}$  or  $>50\%$  reduction from baseline GH on Day 14. The mean serum concentration of GH collected over 6 hours will be used for the baseline (Day -1) and endpoint (Day 14) GH determination.

Several sequential analyses will occur during Stage 1. The Stage 1 arm (BID administration) may be terminated early for futility during each of these interim analyses if the responder rate does not exceed the pre-determined minimum efficacy criteria. In that case, a Stage 2 arm will be initiated during which up to 12 subjects will be recruited to receive BIM23B065 three times a day (TID) for 14 days. The same sequential analysis and early termination rule for futility will apply during Stage 2 as for Stage 1.

Any subjects who withdraw prior to the Day 14 end of treatment visit may be replaced except for early withdrawal due to safety and tolerability reasons. As soon as 12 subjects (out of which at least 8 are Octreotide responders as tested during the screening period) reach Visit 8, withdrawn subjects will not be replaced.

Both the BID and TID regimen parts will consist of 3 periods (See Figure 1):

- A screening period of 21 days maximum during which the eligibility criteria will be assessed. An Octreotide test will be also performed at the latest 7 days prior to first IMP administration.
- A treatment period that will consist of twice or three times daily administrations of BIM23B065. This period will last for 14 days. The first 6 days will be a titration of BIM23B065 (0.4 mg/0.6 mg/0.8 mg BID or TID). Then a stable target dose (1.0 mg) of BIM23B065 will be BID or TID administered from Day 7 to Day 14.
- If during the study, a subject experiences any safety or laboratory events (for detailed description see Table 1 of the Protocol), they may have their dose reduced to the prior dose. The minimum dose allowed for the treatment period is 0.6mg BID or TID.
- If during the titration period, the subject experiences any cardiovascular events that meet the protocol determined criteria (for detailed description see Table 2 of the Protocol), they must remain on their current dose and not be dose escalated.

[figure not shown]
**Protocol code:** D-FR-10380-002

**Protocol Title:** A phase IIA, open-label, single-arm, two stage, multi-centre study to investigate the pharmacodynamics, pharmacokinetics, safety and tolerability of repeated subcutaneous administration of BIM23B065 in subjects with acromegaly

- A follow up period that will last for 14 days during which the subjects will not be administered BIM23B065.

**Figure 1 Study Schema**

## 6.2. Selection of Study Population

The detailed description of the inclusion and exclusion criteria can be found in the study Protocol.

## 6.3. Method of Treatment Assignment and Randomization

No randomisation list will be required for this open-label study. Enrolled subjects will be identified throughout the study with the unique subject number assigned at screening.

## 7. SEQUENCE OF PLANNED ANALYSIS

### 7.1. Data Review Committee (DRC)

Details of the DRC set up, membership, management and responsibilities will be provided in the DRC charter and archived in the TMF. Safety and efficacy data will be summarised and presented to the DRC according to analyses planned in the DRC charter.

## 7.2. Interim Analysis

During Stage 1, two interim analyses are planned after 6 and 8 subjects complete the Day 14 GH assessment. The DRC will meet and review the number of GH responders on Day 14 (i.e. a GH responder is defined as a subject with GH  $\leq 2.5\mu\text{g/l}$  or with at least 50% reduction from baseline GH after 6-day titration plus 8-day treatment with BIM23B065 measured by mean serum concentration of GH over 6 hours at Day 14) as well as the safety and tolerability data defined in the DRC charter.

Based on the safety and efficacy data of these subjects, the DRC will decide if the BID cohort may be continued or stopped, and if stopped, if a TID cohort (Stage 2) may be initiated, according to the following criteria (please see

Figure 2 below).

- If there are less than 3 out of 6 (3/6) responders then the BID regimen (Stage 1) will be stopped for futility and Stage 2 will be initiated, where new enrolled subjects will follow the TID administration part (Option 1 in Figure 2).

If there is at least 3/6 responders, then the Stage 1 will continue: the next 2 subjects will follow the BID administration part and DRC will review the safety and efficacy data once 8 evaluable subjects will have completed Stage 1.

- If there are less than 4 responders (out of 8 subjects) then the BID regimen (Stage 1) will be stopped for futility and Stage 2 will be initiated, where new enrolled subjects will follow the TID administration part (Option 2 in Figure 2).

If there are at least 4 responders (out of 8 subjects), then the Stage 1 will continue: the next 4 subjects will follow the BID administration part and DRC will review the safety and efficacy data once 12 subjects will have completed Stage 1.

- If there are less than 8 responders (out of 12 subjects) then the Stage 2 will be initiated, where new enrolled subjects will follow the TID administration part (Option 3 in Figure 2).

If there are at least 8/12 responders, then no new subjects will be enrolled into the BID administration part, no TID administration part will be conducted and the study will be stopped as the primary objective is met with the BID regimen.

At any time during Stage 1 if at least 3 subjects experienced at least one dose limiting toxicity (DLT) (the definition of DLT can be found in the study protocol Table 3.) then the DRC will stop the recruitment and no TID administration part will be conducted.

During Stage 2, two interim analyses are planned after the first 6 and 8 subjects will have completed the GH Day 14 assessment. The DRC will review safety and efficacy data of these subjects in order to decide if the trial may be stopped early for futility or not (please see Figure below).

**Protocol code:** D-FR-10380-002

**Protocol Title:** A phase IIA, open-label, single-arm, two stage, multi-centre study to investigate the pharmacodynamics, pharmacokinetics, safety and tolerability of repeated subcutaneous administration of BIM23B065 in subjects with acromegaly

If there are less than 3/6 responders, then no new subjects will be enrolled into the TID administration part and the study will stop (Option 1 in Figure ).

If there are at least 3 responders (out of 6 subjects), then the next 2 subjects will follow the TID administration part and DRC will review the safety and efficacy data once 8 subjects will have completed Stage 2.

If there are less than 4 responders (out of 8 subjects) then the TID regimen (Stage 2) will be stopped for futility, no new subjects will be enrolled into the TID administration part and the study will stop (Option 2 in Figure ).

If there are at least 4 responders, then Stage 2 will continue: the next 4 subjects will follow the TID administration part once 12 subjects will have completed Stage 2 and the study will be stopped (Option 3 in Figure ).

Again, at any time during Stage 2 if at least 3 subjects experienced at least one DLT, then the DRC will stop the recruitment.

Figure 2 BID administration part (Stage 1)

[figure not shown]
[figure not shown]

Figure 3 TID administration part (Stage 2)

### 7.3. Monthly blood pressure and 12-lead ECG report

On the second week of each month a report will be created presenting the blood pressure and ECG parameters for all subjects enrolled until the beginning of the month.

Systolic blood pressure, diastolic blood pressure and heart rate will be listed with visit days and time-points. The time-matched change from baseline (the same time-point on Day -1) will be calculated, and listed. Descriptive statistics (n, mean, SD, median, minimum and maximum) will be provided for the scheduled values and changes from baseline at each time point.

ECG parameters (RR interval, PR/PQ interval, QRS interval, QT interval, QTc interval (calculated according to the Fridericia method), and HR) will be listed at each visit and time point, along with their change from the time-matched baseline of Day-1. Descriptive statistics will be provided about the measured values and the calculated change of baseline.

**Protocol code:** D-FR-10380-002

**Protocol Title:** A phase IIA, open-label, single-arm, two stage, multi-centre study to investigate the pharmacodynamics, pharmacokinetics, safety and tolerability of repeated subcutaneous administration of BIM23B065 in subjects with acromegaly

Number and proportion of subjects with absolute QTc values above 460, 480 and 500 msec and subjects with a QTc change more than 30 and 60 msec from baseline will be presented at each time point.

#### **7.4. Final Analyses**

The study can be discontinued prematurely at any time if the Sponsor judges it for any appropriate reason, and for safety reasons, patients will not be dosed further.

In the final analyses all data will be listed for the BID (Stage 1) and TID (Stage 2) treatment regimen separately and summary tables will be created including the results of both stages.

### **8. SAMPLE SIZE DETERMINATION**

A sufficient number of subject will be enrolled so that there is a maximum of 24 evaluable subjects for the primary analysis (12 per stage). Enrolled subjects who drop out of the study prior to Day 14 GH evaluation may be replaced so that 12 are evaluable per Stage. (Replacement strategy is detailed in Section 10.1.).

A minimum of 8 of the 12 evaluable subjects must be responsive to a single test dose of octreotide pre-study defined as a >50% reduction in GH.

Per the primary endpoint, a subject is defined as a responder if the mean concentration of GH over 6 hours is  $\leq 2.5\mu\text{g/l}$  or if there is at least 50% reduction from mean baseline in GH at Day 14 (after 6 days titration plus 8 days treatment).

Based on the exact test for single proportion, twelve evaluable subjects per stage would be sufficient to have over 84% power, at a significance level of 0.05 (one sided) to reject the null hypothesis that there is no indication of efficacy of BIM23B065 if the GH responder rate is at most 33%, assuming that the GH responder rate is equal to 75%.

### **9. ANALYSIS POPULATIONS**

The following populations will be used during statistical analyses:

- Safety population/Intent to treat (ITT): All subjects with at least one IMP administration
- Modified Intent to treat (mITT) population: All subjects in the Safety population with available pharmacodynamic data and no protocol deviations with relevant impact on PD data.

**Protocol code:** D-FR-10380-002

**Protocol Title:** A phase IIA, open-label, single-arm, two stage, multi-centre study to investigate the pharmacodynamics, pharmacokinetics, safety and tolerability of repeated subcutaneous administration of BIM23B065 in subjects with acromegaly

- Efficacy Evaluable (EE) population: All subjects in the mITT population with an evaluable primary efficacy endpoint (mean concentration of GH over 6 hours) at baseline and V8 (+14 days post baseline).
- Per protocol (PP) population: All subjects in the efficacy evaluable (EE) population who complete the study and for whom no major protocol violations/deviations occurred.

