#### 10.1. Methods for Missing Data

A subject is considered evaluable if he or she completes the 14-day treatment period (with 6 hours GH samples collected). Subjects who withdraw from the study before reaching the point of being evaluable may be replaced. If the withdrawal is due to safety and tolerability reasons no replacement will be performed, but otherwise the subject will be replaced. If 12 evaluable subjects have already completed visit 8 (day 14) any subsequent withdrawn subjects will not be replaced.

A minimum of 8 octreotide responders must be evaluable in the final analysis. If an octreotide responder withdraws prematurely, he/she will be replaced by another octreotide responder. If an octreotide non-responder withdraws, they can be replaced by either a responder or non-responder.

No substitution of missing values will be performed, an observed case approach will be used.

In all listings, missing or incomplete dates will be left as they have been recorded. However, for calculation / sorting / assignation based on dates, the following methods will be used:

- The most conservative approach will be systematically considered. For example, if the onset date of an AE/concomitant medication is missing / incomplete, it is assumed to have occurred during the study treatment phase (i.e. a TEAE for AEs) except if the partial onset date or other data (e.g. stop date) indicates differently.
- A missing/incomplete date of medical history or disease diagnosis will be assumed to have occurred before any study treatment.

Where this is possible, the derivations based on a partial date will be presented as superior inequalities (i.e.: for an AE started in FEB2004 after the administration performed on

**Protocol code:** D-FR-10380-002

**Protocol Title:** A phase IIA, open-label, single-arm, two stage, multi-centre study to investigate the pharmacodynamics, pharmacokinetics, safety and tolerability of repeated subcutaneous administration of BIM23B065 in subjects with acromegaly

31JAN2004, the days since last dose will be “≥2”, similarly the duration of ongoing AEs or medication will be “≥xx” according to the start and last visit dates).

If the severity or the relationship to the IMP is not available for an AE it will be marked as ‘unknown’.

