### **11.1. Disposition of Subjects and Withdrawals**

Disposition data will be listed for all subjects who entered this study.

A frequency table will be created displaying disposition of patients including:

- Total number of subjects entered (subjects who gave informed consent);
- Number of screening failures/withdrawals before enrolment
- Number of enrolled subjects
- Number of subjects in the ITT set (subjects who received at least one IMP administration);
- Number of subjects withdrawn after the treatment start date;
- Number of subjects completed the treatment phase;
- Number of subjects completing the study (including follow up);

Withdrawals/Discontinuations during the treatment period will be summarized by the coded term for main reason of withdrawal (patients with a reason recorded as “other” will have an own category). Subjects withdrawn will be listed along with the reason and date of discontinuation.

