## **13. EFFICACY ANALYSIS**

### **13.1. Primary Efficacy Variable Analyses**

The primary efficacy variable is the percentage of subjects who are GH responders on Day 14. GH response is defined as having a mean GH  $\leq 2.5 \mu\text{g/l}$  at Visit 8 (Day 14, after 6-day titration plus 8-day treatment with BIM23B065) or at least a 50% reduction in the mean GH change from baseline on Day 14. The mean serum concentration of GH is calculated at baseline and on Day 14 from the non-missing serum concentrations of GH recorded over 6 hours on these days. The number and proportion (%) of GH responders will be reported with its 90% confidence interval calculated using the exact Clopper-Pearson method. The null hypothesis that the GH responder rate is not clinically relevant (i.e.  $\leq 33\%$ ) will be tested at the one-sided 5% significance level. The exact p-value will be reported. The test will be rejected if the lower 90% confidence limit is larger than 33%. Primary efficacy analysis will be based on the Efficacy Evaluable population.

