#### **13.1.1. Sensitivity and Supportive Analyses for the Primary Efficacy Variable**

The primary efficacy analysis will be repeated on the Per Protocol Population, if the populations are different.

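### The Per Protocol set requires completion of the off-drug follow-up, so a subject lost after Day 14 would leave the only supportive analysis of a Day 14 endpoint

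*SAP*

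**What the plan says.** **The set.** SAP Section 9 builds PP from the EE population by adding two conditions. Members are those "who complete the study and for whom no major protocol violations/deviations occurred". Study completion is thus required in addition to the absence of major deviations.

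**What completion means.** Section 9 does not define it. The disposition table in Section 11.1 has one line for "Number of subjects completed the treatment phase" and a separate line for "Number of subjects completing the study (including follow up"). Section 10.3 ends the treatment phase at Visit 8 and starts follow-up the next day. Section 6.1 describes "A follow up period that will last for 14 days during which the subjects will not be administered BIM23B065", and Section 5.2.6 places the end-of-study visit at Day 28 ("at Day 14 and Day 28 (EoS/ED")).

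**The endpoint.** Section 13.1: "The primary efficacy variable is the percentage of subjects who are GH responders on Day 14". Section 10.1, Methods for Missing Data (printed after Section 10.7): "A subject is considered evaluable if he or she completes the 14-day treatment period (with 6 hours GH samples collected"). EE already requires an evaluable 6-hour GH mean at baseline and Visit 8.

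**Use of the set.** Section 13.1.1 plans one supportive analysis: "The primary efficacy analysis will be repeated on the Per Protocol Population, if the populations are different". Sections 9.1 and 13.2 also use PP for the secondary efficacy endpoints. The GH ones are assessed on Day 7 and Day 14 (Section 13.2.1). IGF-1 is assessed on Day 14 and Day 28 (Sections 5.2.2 and 5.2.5).

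**The concern.** A PP repeat is meant to show the result among subjects treated and measured as planned up to the endpoint. Here, membership also depends on something that happens after the endpoint has been recorded. A subject with full dosing, no major deviation and a complete Day 14 GH profile would leave PP by withdrawing during the drug-free fortnight. That withdrawal cannot change the Day 14 value. It may be related to response or tolerability, though the SAP gives no evidence either way.

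Three features of the plan add to this:

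- PP is the only analysis listed under Section 13.1.1, so nothing else would offset an odd PP result.
- Such a subject is already evaluable, so the replacement rule in Section 10.1 would not bring PP back to 12.
- If no EE subject has a major deviation, follow-up losses alone would make PP differ from EE and so trigger the repeat. It would then say nothing about adherence.

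**Working it through.** **Inputs.** n = 12 evaluable per stage, null rate 33%, assumed rate 75%, one-sided 5% level (Section 8). Exact test with the Clopper-Pearson 90% interval, rejecting if the lower limit exceeds 33% (Section 13.1). The SAP gives no dropout rate between Day 14 and Day 28.

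**Step 1: the plan's own figure.** With X ~ Bin(12, p):

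- P(X ≥ 7 | 0.33) = 0.0632, above 0.05.
- P(X ≥ 8 | 0.33) = 0.0176, so the critical value is 8.
- P(X ≥ 8 | 0.75) = 0.8424, which agrees with the stated power of over 84%.

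**Step 2: effect of post-Day 14 losses on the supportive result.** For x responders among n, the lower limit is the 5% quantile of Beta(x, n − x + 1), and the p-value is P(Bin(n, 0.33) ≥ x).

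| EE result | Lost after Day 14 | PP result | PP lower 90% limit | PP p | Null rejected: EE → PP |
|---|---|---|---|---|---|
| 7/12 (31.5%, p = 0.0632) | one non-responder | 7/11 | 35.0% | 0.0366 | no → yes |
| 8/12 (39.1%, p = 0.0176) | one responder | 7/11 | 35.0% | 0.0366 | yes → yes |
| 8/12 (39.1%, p = 0.0176) | two responders | 6/10 | 30.4% | 0.0732 | yes → no |

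The critical values are 8 of 12, 7 of 11 and 7 of 10. With a single loss from 12, the only route to a changed conclusion is 7/12 with a non-responder lost. Reversing 8/12 takes two losses, both responders.

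**Step 3: how likely the one-loss reversal is.** At a true rate of 75%, P(X = 7) = 0.9456 − 0.8424 = 0.103, ignoring the futility looks. If exactly one of the 12 is then lost at random, the chance that it is one of the five non-responders is 5/12. The joint chance is 0.103 × 5/12 = 0.043, about 4%, given that one loss occurs.

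**Step 4: how likely any such loss is.** With an assumed loss probability d per subject between Day 14 and Day 28, P(at least one of 12) = 1 − (1 − d)^12.

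| Assumed d | P(at least one lost) |
|---|---|
| 2% | 22% |
| 5% | 46% |
| 10% | 72% |
| 20% | 93% |

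PP could therefore differ from EE for this reason alone even at modest dropout. A changed conclusion is much less likely.

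**The case against.** The strongest objections are these.

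- **Nothing decisive depends on PP.** A reader might infer that the primary result or the move from BID to TID is at risk. The SAP does not support that. Section 13.1 bases the primary analysis on EE, which keeps subjects lost after Day 14. Section 7.2 bases the stage rules on Day 14 responder counts: a Stage 1 result of 7/12 leads to Stage 2 whatever PP shows. Section 11.3 lists reasons for exclusion from each population, so a discrepancy would be visible. This objection stands and limits the point to the supportive analysis.
- **Day 28 is not irrelevant to everything PP serves.** IGF-1 below the upper limit of normal is a secondary endpoint at Day 28 as well as Day 14, and PP is used for it. This also stands: the criticism applies to Day 14 endpoints. It does not justify the condition for GH, because under the observed-case rule in Section 10.1 a subject without a Day 28 IGF-1 value is simply absent from that one summary.
- **The meaning of completion is inferred.** Section 9 does not define it, and Section 11.2 leaves PP eligibility to a data review meeting under a Protocol Deviation Handling Plan that is not shown. That is fair, but the only gloss the SAP gives, in Section 11.1, includes follow-up and separates it from completing treatment. At the least, the wording should be settled before results are known.
- **A revised set could duplicate EE.** The modified ITT population, in which EE is nested, already excludes deviations with relevant impact on PD data. Restricting PP's major deviations to those affecting Day 14 would leave PP nearly equal to EE. For that reason the deviation criterion should be left as it is.

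**Conclusion.** The point holds as a minor defect of definition. Read with Section 11.1, the PP definition excludes a subject lost only in the off-drug follow-up from the sole supportive analysis of an endpoint already measured. The primary EE analysis and stage decisions are unaffected.

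The size is conditional. A subject would be dropped only if lost between Day 14 and Day 28, and the SAP gives no rate for this; the 2% to 20% used above are assumptions. With 12 evaluable subjects, one loss reverses the supportive conclusion only from 7/12 with a non-responder lost (31.5% to 35.0%). Two lost responders reverse it from 8/12 (39.1% to 30.4%).

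A reader might also infer that the supportive result would be biased in a known direction. The SAP does not support this: both directions are possible, and no link between follow-up loss and response is documented.

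**What to change.** In the PP definition in Section 9, replace the requirement to complete the study with completion of the treatment period through Visit 8 (Day 14). Leave the criterion of no major protocol violations or deviations exactly as it stands. EE largely implies completion to Visit 8 already, so PP stays distinct from EE through that criterion.

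State that Day 28 IGF-1 is summarised on observed cases within this set. Report completion of follow-up in the disposition table only, where Section 11.1 already has a line for it.

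The cost is one line in Section 9 and a short note to Section 13.2.2. No new data, visits or sample size are needed. The change should be made before results are known.
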